### **8.6 Pharmacodynamics**

Listings will display viral load data at each period/timepoint collected by subject and these data will be presented graphically. Mean and median levels of the viral load will be calculated at each period/timepoint.

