### Study Objectives

The primary objectives of the study are to:

- Evaluate the safety and tolerability of 12 weeks of treatment with a 200 vs. 300 mg PO BID dose of EBP-994 in subjects chronically infected with HDV
- Evaluate the pharmacodynamic (PD) activity of a 200 vs. 300 mg PO BID dose of EBP-994 on HDV viral load
- Evaluate the pharmacokinetic (PK) activity of a 200 vs. 300 mg PO BID dose of EBP-994
- Evaluate the safety, tolerability, PK, and HDV viral load of a treatment up to 48 weeks with EBP-994 alone and in combination with Norvir® and/or Pegasys® in subjects chronically infected with HDV

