### **General**

Demographics of subjects will be described. All reported adverse events will be mapped to standard coding terms (MedDRA) and grouped by system organ class and preferred terms. The incidence of adverse events will be tabulated by seriousness, severity, and relationship to study drug. If an adverse event is reported more than once during the study period, the greatest severity and worst-case attribution will be presented in tables. Adverse events will also be listed for individual subjects, along with information regarding onset, duration, severity, and relationship to study drug. Adverse events that lead to withdrawal from the study will be listed and summarized by treatment group separately. Summary tables and listings of serious adverse events will also be generated. Pharmacodynamic data will be presented in listings and will display viral load data at each period/timepoint collected by subject. These data will also be presented graphically. Mean and median levels of the viral load will be calculated at each period/timepoint.

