### **Pharmacokinetics**

Blood samples will be obtained for pharmacokinetics of EBP-994 at Study Visit 1 (Day 1) and Study Visit 6 (Day 28). Pharmacokinetic parameters for EBP-994 such as maximum concentration ( $C_{max}$ ), area under the time-concentration curve (AUC), time to peak concentration ( $t_{max}$ ), elimination half life ( $t_{1/2}$ ), volume of distribution ( $V_{area/F}$ ) and clearance (CL/F)] will be calculated and tabulated with descriptive statistics. Geometric mean and geometric CV% will be provided for AUC and  $C_{max}$  values.

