### **Pharmacodynamics**

Mean and median levels of the viral load will be calculated.

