### 1.1 Rationale

The IC50 for EBP-994 (formerly lonafarnib) in the H-ras farnesyl transferase inhibition assay is 2.4 nM. Because HDV particle production is dependent on the farnesylation of HDV large delta antigen, EBP-994 is expected to be an inhibitor of the HDV life cycle at the stage of

[figure not shown]
particle production. Indeed, the EC50 for EBP-994 in the HDV virus-like particle (VLP) production assay is 34 pM, consistent with the fact that multiple large delta antigen proteins are contained in a virus or virus—like particle and the hypothesis that inhibiting the farnesylation of only a fraction of the delta antigens can have a trans-dominant effect on particle production. These data suggest that EBP-994 can be a potent inhibitor of the HDV life cycle in vivo. Combined with EBP-994’s favorable safety and tolerability profile demonstrated to date in Phase I through III testing for oncology indications, EBP-994 was therefore hypothesized to be a useful novel way of treating hepatitis delta infections.

Recently, a Phase Ib study of EBP-994 in patient chronically infected with HDV was initiated at the National Institutes of Health (NIH). In the first phase of the study, 8 patients were randomly assigned to drug (6 patients; 100 mg PO BID) vs. placebo (2 patients) for 28 days of treatment. In the second phase, 8 patients will receive either EBP-994 (6 patients; 200 mg PO BID) or placebo for 28 days of treatment. Data on the first seven patients from the first phase of the study is currently available. EBP-994 was well tolerated in all subjects with no SAEs. All patients receiving EBP-994 experienced reductions in HDV viral load during the treatment period, with rebound observed upon cessation of drug treatment (see Figure 2). Three of the 5 patients treated with EBP-994 experienced an approximate 1 log drop or greater in HDV viral load during the 28 day treatment period (Note: patients # 3 and # 7 received placebo).

**Figure 2. Interim analysis of changes in HDV viral load during treatment with 100 mg PO BID EBP-994.** Bar indicates period of treatment with EBP-994 (or placebo).

The mean change in viral load from baseline was directly proportional to the mean drug levels measured in individual patients.

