### **Clinical Safety Summary**

There are currently no HDV-specific therapies. EBP-994 could be the first direct acting anti-HDV agent by disrupting the HDV life cycle through inhibition of prenylation at the level of host cell farnesyl-transferase. EBP-994 has been dosed in human studies examining PK and PD and has exhibited inhibition of farnesyl transferase at levels below the maximally tolerated dose (MTD; 300 mg BID). A risk associated with the use of direct acting antiviral agents would be the development of resistance by the virus. However, because prenylation is a host function not coded for by the HDV genome, the risk of resistance development could be mitigated. Viral surveillance will be conducted throughout the conduct of the study to assess the risk of viral resistance. Two doses of EBP-994 alone, or in combination with Norvir® and/or Pegasys® will be examined in this proof-of-concept study, 200 vs. 300 mg

(PO BID), and the adverse profile will be correlated to the clinical benefit of viral suppression.

Other risks that may be encountered with the treatment of HDV include an increase in liver function tests during and after therapy, the risk of a flare in HBV ( $\geq 1$  log increase in HBV viral load) as the HDV viral load goes down, and an increase in HDV viral load after therapy is ended. Flares in liver function tests are not uncommon with the start of treatment of HBV disease and necessitate a careful and frequent review of liver function studies. We will follow the same approach in this study unless there is a concomitant flare in HBV viral load. A flare of HBV viral load while on EBP-994 will be treated by starting specific anti-HBV therapy using one of the 5 approved drugs, the selection being made by the Investigator based on the subject's condition and history of prior anti-HBV therapy. A flare in HDV viral load after the termination of EBP-994 will be watched closely and interferon therapy may be started as determined by the investigator.

Finally, the known adverse event profile for EBP-994 (and all other prenylation inhibitors in clinic) is primarily gastrointestinal, primarily dose related diarrhea as well as nausea and vomiting.

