## 2 STUDY OBJECTIVES

The primary objectives of the study are to:

- Evaluate the safety and tolerability of 12 weeks of treatment with either a 200 mg po BID dose of EBP-994, or a 300 mg po BID dose of EBP-994, in subjects chronically infected with HDV genotype 1
- Evaluate the pharmacodynamic (PD) activity of a 200 mg po BID dose of EBP-994, vs. a 300 mg po BID dose of EBP-994 on HDV viral load
- Evaluate the pharmacokinetic (PK) profile of a 200 mg po BID dose of EBP-994 vs. a 300 mg po BID dose of EBP-994 in subjects chronically infected with HDV genotype 1
- Evaluate the safety, tolerability, PK, and HDV viral load of a treatment up to 48 weeks with EBP-994 alone, or in combination with Norvir® and/or Pegasys® in subjects chronically infected with HDV

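### HDV viral load is a primary objective in a study randomised to four groups, but its only planned summary statistics are mean and median levels: no log10 change from Day 1, spread, group summary or group difference with a CI

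*Combined protocol and SAP*

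**What the plan says.** The Protocol Summary lists among the primary objectives: "Evaluate the pharmacodynamic (PD) activity of a 200 vs. 300 mg PO BID dose of EBP-994 on HDV viral load". Section 2 repeats the contrast as "a 200 mg po BID dose of EBP-994, vs. a 300 mg po BID dose of EBP-994 on HDV viral load". Both lists add a further primary objective covering viral load over up to 48 weeks on EBP-994 alone or combined with Norvir and/or Pegasys. Sections 3 and 6.2 say that subjects are randomised on Day 1, and Section 6.2 lists four groups.

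The analysis of viral load is described in three places. Section 8.6 plans by-subject listings, graphs and one set of statistics: "Mean and median levels of the viral load will be calculated at each period/timepoint". The General part of the Protocol Summary says the same: "Pharmacodynamic data will be presented in listings and will display viral load data at each period/timepoint collected by subject", with graphs, means and medians. Its Pharmacodynamics part says only: "Mean and median levels of the viral load will be calculated".

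Other parts of the document are more specific. The Rationale in Section 1.1 describes earlier data as log drops and as change from baseline: "The mean change in viral load from baseline was directly proportional to the mean drug levels measured in individual patients". The Clinical Safety Summary in Section 1.2 says that "the adverse profile will be correlated to the clinical benefit of viral suppression". For PK, the Protocol Summary promises: "Geometric mean and geometric CV% will be provided for AUC" and Cmax, and Section 8.5.1 gives a ln-scale model with a 90% CI. Section 8.4.1 summarises adverse events leading to withdrawal by treatment group.

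**The concern.** A reader who carries out Section 8.6 as written obtains levels at each visit and nothing that estimates how far viral load fell in one group compared with another. A level mixes where subjects started with what happened to them, and without a spread measure the reader cannot judge how far a mean can be trusted. The correlation promised in Section 1.2 needs a measure of suppression for each subject, and Section 8 defines none.

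Day 1 pre-dose viral load is collected and listings are by subject, so change could be rebuilt later. The scale, the timepoint, the grouping and the value given to undetectable results would then be chosen with the data in hand, in an open-label study. The value for undetectable results matters because the Rationale expects some subjects to reach undetectability.

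**Working it through.** **1. What is stated for viral load, item by item** (Section 8.6 and the General and Pharmacodynamics parts of the Protocol Summary)

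| Item | Stated for viral load? | Stated elsewhere? |
|---|---|---|
| Listings by subject, graphs | Yes | – |
| Mean and median level | Yes | – |
| Log scale | No | PK: ln scale, geometric mean |
| Change from Day 1 | No | Rationale, for earlier data only |
| Spread | No | PK: geometric CV% |
| Summary by group | No | Withdrawal adverse events |
| Difference or ratio with CI | No | PK: Day 28 / Day 1 ratio, 90% CI |

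**2. Sample size.** There is no figure to reproduce. Up to 75 subjects are planned, and Section 8.7 says that neither an effect nor a variability was assumed. No allocation ratio is given.

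**3. Precision of the missing estimate.** Assumptions: equal allocation, so 75/4 = 18.75, about 19 per group; SD of log10 change from 0.5 to 1.5; no baseline adjustment. The half-width of a 95% CI is t(0.975, 2n−2) × SD × √(2/n).

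- n = 19: 2.028 × 0.3244 × SD = 0.658 × SD, which gives 0.33, 0.49, 0.66 and 0.99 log for SD 0.5, 0.75, 1.0 and 1.5.
- n = 9: 2.120 × 0.4714 × SD = 0.999 × SD, which gives 0.50, 0.75, 1.00 and 1.50 log.

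**4. Where the 200 vs 300 mg BID contrast sits.** These doses are 2 × 200 = 400 and 2 × 300 = 600 mg per day. The daily caps are:

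| Group | Protocol Summary | Section 6.2 |
|---|---|---|
| 1 (monotherapy) | 600 mg | 600 mg |
| 2 (Norvir) | 200 mg | 200 mg |
| 3 (Pegasys) | 600 mg | 200 mg |
| 4 (Norvir and Pegasys) | 150 mg | 200 mg |

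Under the Section 6.2 caps only Group 1 can hold either dose. Under the Protocol Summary caps Groups 1 and 3 can. Neither list makes 200 vs 300 mg BID a randomised contrast. If one group of about 19 is split evenly, 75/4/2 = 9.4, or about 9 per dose, which is the second row of step 3.

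**5. A secondary check: would levels rank two groups correctly?** Assumptions: 19 per group, true mean changes of −1.0 and −1.75 log (a 0.75 log difference), SD of change 0.75, baseline log10 SD 0.75 to 1.0, and each summary set against its own Day 1 value. For mean log10 change the chance of ranking the groups wrongly is Φ(−0.75 / (0.75 × √(2/19))) = Φ(−3.08) = 0.1%. For the median level, simulation gives about 1.5% to 3.6%, depending on the baseline SD and on how change relates to baseline.

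**The case against.** The strongest reply is that this is an open-label pilot. Its objectives are to evaluate, no hypothesis or alpha is stated, and the sample size has no statistical basis, so descriptive reporting is legitimate. That stands against any demand for a powered test. It does not answer the missing change from Day 1, group summary and spread, which are themselves descriptive. The interval is the weakest of the four omissions and should be labelled exploratory.

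A second reply is that Section 8 is terse throughout: Sections 8.3 and 8.4.2 name no grouping either, and listings and graphs by subject are planned. This is fair, and no data are lost. But listings and graphs supply none of the missing items.

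Two stronger readings are tempting and are not supported.

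- A reader might infer that groups will be pooled. Section 8.6 is silent on this. If they were pooled, and one of four equal groups with a mean change 0.75 log smaller than the others' finished early, the pooled mean change would move by 0.75 × 1/4 = 0.19 log with no subject changing. That figure depends on both assumptions.
- A reader might infer that unlogged values will be averaged, which would rank groups less reliably still. No passage says so. If levels are logged first and the same subjects are present, the difference from the Day 1 mean equals mean log10 change, and no ranking is lost.

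The median's disadvantage in step 5 is modest and rests wholly on assumed values. It would be smaller with a narrower baseline spread, which the viral-load entry threshold in Section 4.1 (absent from the Protocol Summary) might produce.

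**Conclusion.** The point holds and should be fixed. For viral load, a primary objective, the plan yields no estimate of any group difference, and the correlation promised in Section 1.2 has no per-subject measure. This follows from the text and needs no assumption.

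The sizes are illustrative. With SD of change 0.5 to 1.5 log and equal allocation, the 95% CI half-width is 0.33 to 0.99 log at 19 per group and 0.50 to 1.50 log at 9 per dose. Group differences could thus be estimated with moderate precision, and the dose contrast only roughly. The ranking and pooling figures are secondary and conditional.

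The documents do not support saying that the study cannot address viral load, since the Day 1 and follow-up samples needed are already planned. The mismatch between dose caps, objectives and randomised groups is a separate inconsistency, but it must be settled before a dose summary can be defined.

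**What to change.** Amend Section 8.6 as follows.

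1. Summarise log10 HDV RNA change from Day 1 pre-dose by randomised group, with n, mean, SD and median at each timepoint.
2. Report between-group differences adjusted for the Day 1 log10 value, with 95% CIs, labelled exploratory, at Day 28. Treatment lasts 4 to 48 weeks, so Day 28 is the one pre-specified timepoint that all groups share. Give later visits descriptively by group, with n.
3. State one fixed value for undetectable results, and report the proportion undetectable.
4. Analyse by randomised group whatever licensed medication is added or dose reduced (Section 3 allows both), and show the number of such subjects by group and visit.
5. Report 200 vs 300 mg BID by assigned starting dose within the same treatment group, labelled non-randomised unless dose was randomised.
6. Use each subject's log10 change for the correlation promised in Section 1.2.

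Separately, the Group 3 and Group 4 daily caps in the Protocol Summary and Section 6.2 must be reconciled, as must the 200 vs 300 mg BID objectives with the randomised groups.

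The cost is wording in the statistical section and modest programming, with no new visits, samples or subjects. There are two downsides: the mean change will depend on the value used for undetectable results, and the dose contrast will have wide intervals.

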### **8.7 Sample Size And Power**

The sample size has not been determined by strict statistical considerations. From a safety, pharmacokinetic and pharmacodynamic perspective, no a-priori assumptions are made as to the expected treatment effect and associated variability.

### **8.8 Interim Analyses**

No interim analyses are planned.

### **8.9 Missing Data And Data Imputation**

No missing safety or pharmacodynamic data will be estimated.

## **9 ACCESS TO SOURCE DOCUMENTS**

The investigator will make the source documents for this trial available to the sponsor or its representatives, or to the regulatory authority or health authority inspectors.

Subject medical information obtained as a result of this study is considered confidential and disclosure to third parties other than those noted below is prohibited. All reports and communications relating to subjects in this study will identify each subject only by their initials and number. Medical information resulting from a subject's participation in this study may be given to the subject's personal physician or to the appropriate medical personnel responsible for the subject's welfare. Data generated as a result of this study are to be available for inspection on request by government regulatory agency auditors, the Sponsor Clinical Monitor (or designee), and the Institutional Review Board/Ethics Committee (IRB, EC).

The information developed in this clinical study will be used by the Sponsor in the clinical development of the study medication and therefore may be disclosed by the Sponsor as required for disclosure as a public company to other clinical investigators, to other pharmaceutical companies, and/or to other government agencies.

Any information, inventions, or discoveries (whether patentable or not), innovations, suggestions, ideas, and reports, made or developed by the Investigator(s) as a result of conducting this study shall be promptly disclosed to the Sponsor and shall be the sole property of the Sponsor. The Investigator agrees, upon the Sponsor's request and at the Sponsor's expense to execute such documents and to take such other actions, as the Sponsor deems necessary or appropriate to obtain patents in the Sponsor's name covering any of the foregoing.

The investigator will retain all study documents for at least 2 years after the last approval of a marketing application in an ICH region (i.e., United States, Europe, or Japan), and until there are no pending or contemplated marketing applications in an ICH region. If no application is filed or if the application is not approved for such indication, the investigator will retain all study documents for at least 2 years after the investigation is discontinued and regulatory authorities have been notified.

The investigator will notify the sponsor prior to destroying any study records. Should the investigator wish to assign the study records to another party or move them to another location, the sponsor must be notified in writing in advance.

If the investigator cannot guarantee this archiving requirement at the study site for any or all of the documents, special arrangements will be made between the investigator and the sponsor for storage. If source documents are required for continued care of the subject, then appropriate copies for storage off site will be made.

## **10 QUALITY CONTROL AND QUALITY ASSURANCE**

Study monitors will periodically audit, at mutually convenient times during and after the study, all CRFs and corresponding office and clinical laboratory records for each subject. The monitoring visits provide the sponsor with the opportunity to evaluate the progress of the study, to verify the accuracy and completeness of CRFs, to resolve any inconsistencies in the study records, and to assure that all protocol requirements, applicable regulations, other requirements, and investigator's obligations are being fulfilled.

## **11 ETHICS**

### ***11.1 Declaration of Helsinki***

The study will be conducted in accordance with the Declaration of Helsinki (1964) including all amendment up to and including the Scotland revision (2000) as described in Appendix D.

### ***11.2 Institutional Review Board/Ethics Committee***

The protocol, informed consent form, and any materials (such as advertisements, subject information sheets, or descriptions of the study used to obtain informed consent) for this study will be reviewed and approved by a duly constituted institutional review board (IRB)/ethics committee (EC).

The investigator will ensure that all aspects of the IRB/EC review are conducted in accordance with current institutional, local, and national regulations. A letter documenting the IRB/EC approval will be provided to the sponsor prior to initiation of the study. Amendments to the protocol will be subject to the same requirements as the original protocol. The Investigator will submit all periodic reports and updates that the IRB/EC may require, including any final close out reports. The Investigator will inform the IRB/EC of any reportable adverse events.

### ***11.3 Informed Consent***

Each subject will be provided with oral and written information describing the nature and duration of the study, in a language they can understand, and must consent in writing to participate before undergoing screening. The date of the consent shall be entered by the subject. The original signed consent form will be retained with the study center's records. Each subject will also be given a copy of his/her signed consent form.

## **12 DATA HANDLING AND RECORDING**

Data for each subject will be recorded on the CRF using indelible black ink. CRFs must be completed for every subject who signs an informed consent and has screening procedures performed.

The investigator is responsible for the completeness and accuracy of information collected on the CRFs for each individual enrolled. The CRFs will be signed and dated by the investigator.

If an entry on a CRF requires change, a single line will be drawn throughout the incorrect entry, the correction will be entered, initialed, and dated. White-out, erasures, or obliterations on CRFs or on source data are not permitted.

The sponsor or designee will conduct data processing. Completed CRFs will be reviewed carefully for accuracy and completeness. If necessary, the study site will be contacted for corrections and/or clarifications. All data will be entered into a study database for analysis and reporting. Any data captured electronically (such as laboratory data) will be transferred electronically to the database. Upon completion of data entry, the database will receive a quality assurance check to ensure acceptable accuracy and completeness.

